- I agree to maintain all information supplied by MingSight Pharmaceuticals Inc. in confidence and, when this information is submitted to an Institutional Review Board (IRB), Independent Ethics Committee (IEC) or another group, it will be submitted with a designation that the material is confidential.

Printed Name of Investigator

Signature of Investigator

Date

SYNOPSIS

Name of Sponsor/Company: MingSight Pharmaceuticals, Inc.

Name of Investigational Product: MS-553

IND Number: 135339

Title of Study: A Phase I/II Dose-Escalation and Expansion Study of the Selective PKC-β Inhibitor MS-553 in Patients with Chronic Lymphocytic Leukemia/Small Lymphocytic Lymphoma

Phase: I/II

Comparator: None

Number of Subjects: Approximately 153

Study Sites: Up to approximately 15 sites

Study Design:

Single agent MS-553 cohorts (A-series):

This is a Phase I/II multi-center, open-label study of MS-553 in patients with chronic lymphocytic leukemia (CLL)/small lymphocytic leukemia (SLL). The first part of the study, the dose escalation portion **(Cohort A1**), will determine the safety of MS-553 and the maximum tolerated dose (MTD) or initial recommended Phase 2 dose (RP2D) of MS-553 monotherapy. After the MTD or initial RP2D is identified, an expansion cohort (**"Expansion Cohort A2**") of approximately 25 patients with refractory or relapsed CLL/SLL who (a) have failed at least two prior lines of therapies, or (b) have either acquired clinical and/or molecular resistance to a BTK inhibitor (i.e., BTK and/or PLCG2 mutation) after achieving initial response to a BTK inhibitor will be enrolled.

In addition, an **optional expansion cohort** ("**Expansion Cohort A3**") of approximately 25 patients with aggressive lymphoma, including Richter's transformation, diffuse large B-cell lymphoma (DLBCL) and mantle cell lymphoma (MCL) may be enrolled. At least 15 patients in this cohort shall be MCL patients.

additional patients will be enrolled in Cohort A2 to allow testing of two dose levels before a final RP2D can be declared.

The two dose schedules, designated as dose schedule 1 (DS1) and dose schedule 2 (DS2), are as follows:

Dose Schedule 1 (DS1)				
MS-553 Oral Daily Dose				
Week 1 150 mg BID				
Week 2 200 mg BID				
Week 3 and beyond 250 mg BID				
Dose Schedule 2 (DS2)				

	MS-553 Oral Daily Dose
Cycle 1 and beyond	225 mg BID

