Twenty of the 40 additional patients will be treated with DS1 and the other 20 patients with DS2. The patients will be allocated to either dose schedule in alternate fashion according to the sequence of their enrollment. For example, the first enrolled patient will be allocated to DS1, the second patient to DS2, the third patient to DS1, the fourth to DS2, and so on.

The optional expansion cohort (Cohort A3) will be closed to accommodate the new dose testing plan.

Combination Cohorts

Combination Cohorts with acalabrutinib (B-series)

As soon as the MTD or initial RP2D is declared for MS-553 monotherapy in Cohort A1, MS-553 will be evaluated in combination with acalabrutinib.

Cohort B1.The first part of the study will be a determination of MTD or initial RP2D of MS-553 when combined with acalabrutinib in treatment experienced CLL/SLL patients who are BTK inhibitor naïve, eligible for standard of care treatment with a BTK inhibitor as a single agent and who have had no more than 2 previous lines of treament regimens. The number of patients in the dose escalation will range from 3 to approximately 12 patients, and start with a MS-553 dose of 150 mg BID in the first dose level. Once the MTD or initial RP2D of MS-553 is known for the combination, two expansion cohorts (B2 and B3) will be started to further evaluate the safety of the combination regimens, as well as to assess early evidence of antitumor activity as described below.

Cohort B2. Once the MTD/ intial RP2D is established in Cohort B1 for MS-553 in combination with acalbrutinib, an expansion cohort will be opened. This cohort will evaluate MS-553 in combination with acalabrutinib in treatment experienced CLL/SLL patients who are BTK inhibitor naïve, are eligible for treatment with a BTK inhibitor as a single agent, and who have had no more than 2 previous lines of treatment regimens. Approximately 20 patients will be

enrolled in Cohort B2 to further confirm the safety of the combination and assess early evidence of anti-tumor activity.

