After the MTD or initial RP2D is identified, an expansion cohort ("**Expansion Cohort A2**") of approximately 25 patients with refractory or relapsed CLL/SLL who (a) have failed at least two prior lines of therapies, or (b) have acquired clinical and/or molecular resistance of a BTK inhibitor (i.e., BTK and/or PLCG2 mutation) after achieving initial response to a BTK inhibitor will be activated.

In addition, an **optional expansion cohort (Cohort A3)** of approximately 25 patients with aggressive lymphoma, including Richter's transformation, DLBCL and MCL, can be activated simultaneously with the activation of the two expansion cohorts. At least 15 patients in this cohort shall be MCL patients.

Patients in the expansion cohorts will be treated at the MTD (or initial RP2D).

All patients will continue to be monitored for approximately 30 days (+7 days) after treatment discontinuation for development of any late treatment emergent adverse events. Any such late adverse events will be considered in the determination of the maximum tolerated dose/initial RP2D and dose schedule to be taken forward into the expansion phase of the study.

additional patients will be enrolled in Cohort A2 to further testing two dose levels before a final RP2D can be declared.

The two dose schedules designated as dose schedule 1 (DS1) and dose schedule 2 (DS2) are as follows:

Dose Schedule 1 (DS1)

	MS-553 Oral Daily Dose	
Week 1	150 mg BID	
Week 2	200 mg BID	
Week 3 and beyond	250 mg BID	

Dose Schedule 2 (DS2)

	MS-553 Oral Daily Dose
Cycle 1 and beyond	225 mg BID

Twenty of the 40 additional patients will be treated with DS1 and the other 20 patients with DS2. The patients will be allocated to either dose schedule in alternate fashion according to

the sequence of their enrollment. For example, the first enrolled patient will be allocated to DS1, the second patient to DS2, the third patient to DS1, the fourth to DS2, and so on.

The optional expansion cohort (Cohort A3) will be closed to accommodate the new dose testing plan.

Cohort B

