Duration of treatment: Patients may continue receiving study drug provided they continue to tolerate the drug, have no evidence of progression, do not meet any of the criteria for discontinuation, and the patients' participation in the study has not ended. The anticipated median treatment duration is unknown.

Reference therapy, dosage and mode of administration:

Not applicable.

Statistical methods:

Summary statistics will be provided for all endpoints. Statistics will be reported according to intention-to-treat (ITT), per-protocol, and per-dose-level. The safety summary statistics will include any patient who received at least one dose of study drug.

Patient characteristics will be described and summarized for each dose level and in total.

Because disease-relevant pharmacodynamics biomarkers are not yet established, and some limited toxicity and pharmacokinetic data in healthy subjects exists, dose escalation will be guided by toxicity.

There is no formal hypothesis to be tested in this study; therefore, no predefined sample size calculation has been made for the efficacy or exploratory endpoints.

The protocol details dose modifications (i.e., reductions, interruptions) that may be warranted as a consequence of drug-related toxicities. At a starting dose level of 100 mg BID (Dose Level 0), no dose reduction is anticipated as monotherapy. If unacceptable toxicity presents during Cycle 1 at Dose Level 0 then the patient will be instructed to discontinue treatment with MS-553. If a patient experiences potential drug-related toxicity, the appropriate dose modification may be implemented until the toxicity has adequately resolved or improved to Grade 1. If unacceptable toxicity presents, then the patient will be instructed to discontinue treatment with MS-553.

Formal stopping criteria are specified in Section 7.13. Since the study is unblinded, the Precision Oncology medical monitor, the Safety Review Committee, the relevant MS-553-103 Investigator(s), and the Sponsor will closely review available safety and PK data on an ongoing basis throughout the dose escalation and dose expansion segments of the open-label study.

TABLE OF CONTENTS, LIST OF TABLES, AND LIST OF FIGURES

TABLE OF CONTENTS

SYNOPSIS		4
TABLE OF C	CONTENTS, LIST OF TABLES, AND LIST OF FIGURES	8
LIST OF AB	BREVIATIONS AND DEFINITIONS OF TERMS	4
1.	INTRODUCTION	7
1.1.	Chronic Lymphocytic Leukemia	7
1.1.1.	B Cell Receptor (BCR) Signaling Inhibitors	7
1.1.2.	Protein Kinase C and PKC-β	8

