3.1.1. Cohort A: MS-553 Monotherapy

The first part of the study, the dose escalation portion (Cohort A1), will determine the safety of MS-553 and the MTD or initial RP2D. After the initial RP2D is identified, an expansion cohort (Cohort A2) will be started at the MTD or initial RP2D, enrolling approximately 25 patients with relapsed/refractory CLL/SLL who (a) have failed at least two prior lines of therapies, or (b) have either acquired clinical and/or molecular resistance to a BTK inhibitor (i.e., BTK and/or PLCG2 mutation) after achieving initial response to a BTK inhibitor. In addition, an optional expansion cohort (Cohort A3) of approximately 25 patients with aggressive lymphoma, including Richter's transformation, DLBCL and MCL will be enrolled. At least 15 patients in Cohort A3 shall be MCL patients.

additional patients will be enrolled in Cohort A2 to further testing two dose levels before a final RP2D can be declared.

The two dose schedules designated as dose schedule 1 (DS1) and dose schedule 2 (DS2) are as follows:

	MS-553 Oral Daily Dose
Week 1	150 mg BID
Week 2	200 mg BID
Week 3 and beyond	250 mg BID

Dose Schedule 1 (DS1)

Dose Schedule 2 (DS2)

	MS-553 Oral Daily Dose
Cycle 1 and beyond	225 mg BID

Twenty of the 40 additional patients will be treated with DS1 and the other 20 patients with DS2. The patients will be allocated to either DS1 or DS2 in alternating fashion, according to the sequence of their enrollment. For example, the first enrolled patient will be allocated to DS1, the second patient to DS2, the third patient to DS1, the fourth to DS2, and so on.

The optional expansion cohort (Cohort A3) will be closed to accommodate the new dose testing plan.

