During the dose escalation period, intra-patient dose escalation will be permitted at the discretion of the study investigators and after discussion with the medical monitor and Sponsor, if the following criteria are met:

- The next higher dose for the regimen has been demonstrated to be safe by at least 3 patients and all 3 patients complete one cycle without experiencing any DLT.
- 2. The patient who will receive the higher dose has not experienced a DLT and has also completed at least 2 cycles of therapy at their current dose.
- 3. Intra-patient dose escalation can be increased only by one dose level at a time.

After completion of each dose escalation cohort, the SRC will review clinical safety and tolerability data as well as PK data available at the time for all patients in order to confirm dose escalation to the next dose level. Based on the SRC's review, a cohort may be expanded, or an intermediate or a lower-than-planned dose level or an alternative dosing schedule may be evaluated.

All patients will continue to be monitored for approximately 30 days (+7 days) after treatment discontinuation for development of any late treatment emergent adverse events. Any such late adverse events will be considered in the determination of the MTD/initial RP2D and dose schedule to be taken forward into the expansion phase of the study.

While the

MTD was not reached, an initial RP2D was identified. **Second Second** the SRC reviewed all available efficacy, safety, PK and PD data of Cohort A1 and some Cohort A2 patients and agreed on an updated RP2D with a ramp-up dosage regimen as shown in Table 3 below.

MS-553	Oral Daily Dose
Weeks 1 to 4 (Cycle 1)	150 mg BID
Weeks 5-8 (Cycle 2)	200 mg BID
Weeks 9 and beyond	250 mg BID
(Cycle 3+)	

Table 3:Initial Recommended Phase 2 Dose

The two new dose schedules are designated as dose schedule 1 (DS1) and dose schedule 2 (DS2) are as follows:

Dose Schedule 1 (DS1)

	MS-553 Oral Daily Dose
Week 1	150 mg BID
Week 2	200 mg BID
Week 3 and beyond	250 mg BID

Dose Schedule 2 (DS2)

	MS-553 Oral Daily Dose
Cycle 1 and beyond	225 mg BID

Twenty of the 40 additional patients will be treated with DS1 and the other 20 patients with DS2. The patients will be allocated to either DS1 or DS2 in alternating fashion, according to the sequence of their enrollment. For example, the first enrolled patient will be allocated to DS1, the second patient to DS2, the third patient to DS1, the fourth to DS2, and so on.

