6.1. Description of Study Procedures

6.1.1. Patient Enrollment and Treatment Assignment

Patient eligibility will be established at the conclusion of the Screening evaluations. During the dose escalation phase, assignment to dose level will be sequential and as described in Section 5.2 Treatment Plan. For the dose expansion phase, patients will be dosed at the MTD or initial RP2D identified during dose escalation.

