6.2.2. Efficacy

Response assessments will be made by the individual investigators. Response for CLL will be evaluated according to criteria published by 2008 IWCLL. Because of the well-documented lymphocytosis not associated with disease progression that occurs with BCR signaling inhibitors such as BTK inhibitors, progressive lymphocytosis in the absence of other signs of disease progression (e.g., splenomegaly, enlarging lymph nodes, and disease-related constitutional symptoms) will not be considered disease progression. Isolated lymphocytosis in the context of what would otherwise be a PR is defined as a PR with lymphocytosis (noted as PR-L, PR+L, or PRwL in literature). Response criteria in the SLL patients and aggressive lymphoma patients will be based on the International Working Group consensus response evaluation criteria in lymphoma (RECIL 2017).

Initial evaluation of the efficacy endpoints related to response will incorporate the data from the first 9 cycles of treatment. Any patient who receives at least one dose of study therapy is evaluable for response. Patients who have stable disease or a response by 9 cycles and continue treatment after 9 cycles will have response assessments including CT scans of the chest, abdomen, and pelvis (and neck if involved), preferably least every 12 weeks, or as clinically indicated until disease progression. Patients who do not have a response by 9 cycles but who have stable disease are eligible to stay on study treatment for up to a total of 24 cycles, with continue to have stable disease after 24 cycles or have a response after 9 cycles therapy, drug therapy can continue until disease progression.

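### The 40 added Cohort A2 patients are assigned to DS1 or DS2 by open alternation with no concealment described, so the contrast that precedes the final RP2D is exposed to selection bias

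*Combined protocol and SAP*

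**What the plan says.** The allocation rule appears four times: twice in the Synopsis (Study Design; Study Design and Methodology, Cohort A), in Section 3.1.1 and in Section 3.3.2. The Synopsis wording is "The patients will be allocated to either dose schedule in alternate fashion according to the sequence of their enrollment". Section 3.1.1 has patients "allocated to either DS1 or DS2 in alternating fashion, according to the sequence of their enrollment". Each place gives the order: first patient DS1, second DS2, third DS1, fourth DS2, and so on, with 20 patients per schedule.

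The Synopsis gives the purpose: "additional patients will be enrolled in Cohort A2 to allow testing of two dose levels before a final RP2D can be declared".

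Section 6.1.1, which covers enrolment and treatment assignment, does not mention DS1 or DS2. It says "For the dose expansion phase, patients will be dosed at the MTD or initial RP2D identified during dose escalation", and it does not say when a patient's schedule becomes known relative to the eligibility decision. The study is open-label at up to about 15 sites. On response, Section 6.2.2 says "Response assessments will be made by the individual investigators".

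**The concern.** Alternation is deterministic. If the person deciding whether and when to enrol a patient knows which schedule comes next, a fitter or frailer patient can be brought forward or held back to match it, deliberately or not. A DS1/DS2 difference in tolerability or response can then reflect who was enrolled rather than the schedule.

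The two groups exist to inform the choice of final RP2D, so they will be set side by side even though the plan specifies no formal comparison. Section 8.1 already calls for summaries by dose level.

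The Synopsis (Statistical methods) gives one possible route by which the order could become known. The sponsor, the relevant investigators, the Safety Review Committee and the medical monitor, it says, "will closely review available safety and PK data on an ongoing basis throughout the dose escalation and dose expansion segments of the open-label study". Section 3.5 puts Principal Investigators on that committee. Neither place says that they see the enrolment order, and neither says that it is withheld.

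**Working it through.** **1. The plan's own figure.** Odd positions to DS1 and even positions to DS2 over 40 enrolments gives 20 and 20. The stated split reproduces.

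**2. How predictable is the next schedule?**
- With the running order known: 100%. The same holds for site staff if the alternation is run within each site, which the plan does not exclude.
- With one sequence across *k* equal sites, and a site that sees only its own patients: the best guess is the opposite of the site's own last assignment. It is right when the gap to that patient is an odd number of enrolments. The probability is (1/k) / [1 − (1 − 1/k)²] = 1/(2 − 1/k). For k = 15 (the plan's upper limit) this is 1/1.933 = 0.517. For k = 5 (assumed) it is 1/1.8 = 0.556.
- For comparison, with every earlier assignment known, simulation gives about 70% for random blocks of 2, 4 and 6, and about 59% for a 20/20 random allocation rule.

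**3. What steering does to the estimate.** The documents give no response rates, so these are assumed: two equally common prognostic groups with ORR 60% and 30%, and no true schedule effect. In a share *s* of slots, DS1 always receives a good-prognosis patient and DS2 a poor-prognosis one.
- Good-prognosis share: 0.5 + s/2 on DS1 and 0.5 − s/2 on DS2.
- False ORR difference: s × (0.60 − 0.30).

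| Share steered | ORR DS1 / DS2 | False difference | P(DS1 at least 3 more responders of 20) |
|---|---|---|---|
| 0% | 45.0% / 45.0% | 0 | 21% |
| 10% | 46.5% / 43.5% | 3 points | 27% |
| 25% | 48.75% / 41.25% | 7.5 points | 38% |
| 50% | 52.5% / 37.5% | 15 points | 57% |

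The last column is exact, from two independent binomials with n = 20. Three of 20 is 15 points.

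**4. Linking predictability to bias.** If sites steered every slot on a guess that is right with probability *g*, the prognostic shares would differ by 2g − 1. With own-site knowledge only:
- 15 sites: 0.034 × 30 points = 1.0 point.
- 5 sites: 0.111 × 30 points = 3.3 points.

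The 7.5- and 15-point rows therefore require the running order to be known where patients are enrolled.

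**5. Set against chance.** SE = √(2p(1 − p)/20), which is 15.5 points at p = 0.40 and 15.7 at p = 0.45. The 95% half-width is 30 to 31 points.

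**6. Would a baseline table reveal it?** If the steered factor is recorded, a Fisher test at p < 0.05 flags 4%, 20% and 87% of trials at 10%, 25% and 50% steering when the number of steered slots is fixed. The rates are 5%, 23% and 83% when patients are drawn independently, as in the table above. Steering on an unrecorded trait would not show.

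**The case against.** The strongest reply is that foreseeability may be close to chance. The wording reads as one sequence across the study, and nothing says that sites are shown it. On own-site knowledge the false difference is only about 1 to 3 points, small beside a standard error of 15.5. This stands as a limit on size: the larger figures hold only if the order is known where patients are enrolled. It does not close the point, because the plan leaves open whether alternation runs centrally or by site and does not say that the order is withheld.

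Second, no primary endpoint is affected. Section 2.4 ties the primary safety endpoint to the DLT periods of A1, B1 and C1. Section 8.4 states no hypothesis, and Section 8.2 claims no power between cohorts. This limits the consequence, and chance alone gives DS1 a lead of 15 points or more in 21% of trials. It does not remove the bias, which is systematic and would not shrink with more patients.

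Third, Section 3.5 describes the committee's monitoring for the escalation segment only. That is so, but the Synopsis extends review of safety and PK data through expansion. It remains a possible route, not a demonstrated one.

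Fourth, text just before the sentence on the additional patients is missing from the public version, and the Pharmacy Manual is not available. The absence of concealment is judged on the visible text, although the allocation sentences and Section 6.1.1 read as complete.

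Finally, unblinded response assessment by investigators is a separate source of bias that concealed allocation would not cure.

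**Conclusion.** The point holds. The plan states a non-random, foreseeable allocation method and describes no concealment, for a two-group contrast that feeds the final RP2D.

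The size depends on who knows the order. Under the assumed 60%/30% response rates, the false ORR difference is about 1 to 3 points if sites know only their own patients, and up to 15 points if half the slots are steered with the order known. Modest steering would usually escape a baseline check. No actual steering is shown. Because sampling error is large and the contrast is descriptive, this is a change that should be made rather than a flaw that invalidates the study.

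**What to change.** Replace the alternation sentences in both Synopsis locations and in Sections 3.1.1 and 3.3.2 with wording such as: *The 40 patients will be randomised 1:1 to DS1 or DS2 from a central concealed list; the schedule is released only after eligibility is confirmed and the patient is registered.*

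- **List.** Unstratified permuted blocks of 2, 4 and 6 in random order, chosen to total 40, keep exactly 20:20. A 20/20 random allocation rule does the same and is harder to guess. If stratification by BTK-inhibitor resistance is preferred, say approximately 20 per schedule.
- **Section 6.1.1.** Reconcile it with the DS1/DS2 plan, and state when the schedule is revealed. Section 5.4 allows replacement of patients but does not say which schedule a replacement receives; state this too.
- **Reporting.** Give baseline characteristics, discontinuation for TEAE, dose intensity and ORR by allocated schedule, with the DS1 minus DS2 difference and its 95% CI.
- **If enrolment has begun.** Randomise the remaining patients, report the allocation method for each patient, and treat the alternated part as non-randomised.

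The cost is one central list and wording changes in five places, with the same patients and visits. The protocol documents an EDC but not a randomisation function in it, so a separately held list or service may be needed. Stratifying would miss exact 20:20 in about one third to one half of simulated trials, nearly always as 21:19. A mid-course change would leave two allocation methods in one cohort.
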